6.3. Early Termination Visit and Follow-up Visit

All patients withdrawing from the study prior to Week 52 will complete an Early Termination visit. The Early Termination visit procedures are identical to those of Week 52; however, for patients whose last dose of study drug is during Week 32 or earlier, the following procedures do not need to be performed: transvaginal ultrasound (with or without a transabdominal ultrasound), bone densitometry, and endometrial biopsy. These procedures may be performed at the investigator's discretion if they aid in follow-up of ongoing adverse events.

Patients (including those who complete the Week 52 visit and those who withdraw early from this study) will have a Follow-up visit approximately 30 days after the last dose of study drug, or prior to the date of initiation of another investigational agent or hormonal therapy affecting the hypothalamic-pituitary-gonadal axis or surgical intervention or other invasive procedure for uterine fibroids, whichever occurs first. However, for patients who enroll directly into another relugolix clinical study upon completion of the Week 52 visit, then the Follow-up visit may be waived.

The Follow-up visit will be used to assess safety after discontinuation of study treatment including adverse events, clinical safety laboratories, and return of menstruation. Refer to the Schedule of Activities (see Section 1.1) for individual study visit procedures during the Follow-up visit.

At an Early Termination visit occurring on or after Week 36, patients with a bone mineral density loss of > 3 relative to the parent study Baseline measurement will undergo a follow-up bone densitometry scan at 6 (± 1) months and will be contacted to question them about medications and conditions (eg, pregnancy) that might affect bone mineral density through the time of follow-up bone densitometry. If Early Termination occurs prior to Week 36, follow-up bone densitometry will be performed according to the requirements of the parent study. The follow-up bone densitometry will be submitted for central reading.

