6.4. Continuation into Randomized Withdrawal Study

Eligible patients may enter the 52-week randomized withdrawal study (MVT-601-035), which is conducted under a separate protocol. Patients will provide separate informed consent to participate for Study MVT-601-035, which will enroll patients who responded to study treatment

in this study and randomize them to receive relugolix 40 mg co-administered with 1 mg estradiol and 0.5 mg norethindrone acetate, or placebo.

6.5. **Unscheduled Visits**

Unscheduled visits may be performed at any time during the study whenever necessary to assess for or follow-up on adverse events, at the patient's request, or as deemed necessary by the investigator. The date and reason for the Unscheduled visit should be recorded in the source documentation. The following activities should be completed at Unscheduled visits: recording of reason for the visit, concomitant medication review, and evaluation of adverse events. In addition, procedures such as vital signs, weight, symptom-directed brief physical examination, central safety laboratory assessment, urine pregnancy testing, pharmacodynamic sampling, 12-lead ECG, study drug compliance and dispensation, etc, may be conducted as needed. See the Schedule of Activities (Section 1.1) for tests that may be performed, as indicated by the reason for a visit, at an Unscheduled visit. The investigator should consult with the medical monitor, if needed, to discuss Unscheduled visit testing. The investigator should obtain approval from the sponsor to perform transvaginal ultrasound, endometrial biopsy, or DXA, unless urgently indicated.

6.6. **Study Procedures**

6.6.1. **Efficacy-Related Procedures**

6.6.1.1. **Menstrual Blood Loss as Assessed by the Alkaline Hematin Method**

The volume of menstrual blood loss is measured in milliliters using the alkaline hematin method [Hallberg, 1964]. The method involves pummeling used feminine products in a solution and measuring the resulting hematin absorbance against calibration curves. The method is validated in accordance with current FDA Guidance for Method Validations and is an accepted quantitative clinical endpoint for the assessment of heavy menstrual bleeding. The site staff will provide collection kits with standardized and validated feminine products to patients for the collection and assessment of those products to determine menstrual blood loss.

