2. STUDY DESIGN

2.1. Summary of Study Design

The LIBERTY EXTENSION study is an international phase 3 open-label, single-arm, long-term efficacy and safety extension study that will enroll eligible patients who have completed their participation in one of the phase 3 randomized, double-blind, placebo-controlled parent studies (MVT-601-3001 or MVT-601-3002). All patients will receive oral relugolix 40 mg once daily co-administered with low-dose estradiol 1 mg and norethindrone acetate 0.5 mg for 28 weeks.

Approximately 600 women with heavy menstrual bleeding associated with uterine fibroids will be enrolled. The objectives of the study are to evaluate long-term efficacy and safety through up to 52 weeks of treatment (including treatment during the parent study) with relugolix co-administered with low-dose estradiol/norethindrone acetate. Eligible patients will have completed participation in one of the parent studies and consented to participate in this extension study.

Screening and baseline procedures will be done at the same visit for this extension study (referred to as the “Week 24/Baseline visit” in this study), which coincides with the Week 24 visit from the parent study and will be defined as the date of completion of the last Week 24 procedure in the parent study.

Patients will have received their last dose of study drug in the parent study on the day prior to the Week 24/Baseline visit and will receive their first dose of study drug for this extension study in the clinic after the patient is determined to be eligible for this extension study and has provided informed consent to participate. Study participants will then take the open-label study treatment (relugolix 40 mg co-administered with estradiol 1 mg and norethindrone acetate 0.5 mg) orally once daily for 28 weeks.

At the Week 36 visit and Week 52/Early Termination visit, each patient will have an assessment of bone mineral density (BMD) by DXA.

Patients who complete the study and are eligible may be enrolled in study MVT-601-035 at Week 52 visit after all Week 52 procedures for the MVT-601-3003 study have been completed. Patients who enroll directly into the MVT-601-035 study upon completion of the Week 52 visit will have the Follow-up visit and the follow-up procedures performed under this protocol, including the follow-up bone densitometry scan at 6 (\pm 1) months and status of menstruation recovery.

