4.3.5. Definition of Treatment Duration

Overall treatment duration is defined as the duration of time from the date of the first dose of parent study drug to the date of the last dose of extension study drug as follows:

$$(\text{Date of last dose of extension study drug} - \text{Date of first dose of parent study drug}) + 1$$

For patients missing day and month for date of last dose of extension study drug, the last date extension study drug was dispensed will be used to calculate treatment duration. For patients missing only day for date of last dose of extension study drug, the later of first of the month of

last dose of extension drug or last date extension study drug was dispensed will be used to calculate treatment duration.

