9.1. Adverse Events

Adverse events will be collected from the time of the first dose of open-label study drug through the safety follow up visit approximately 30 days after the last dose of open-label study drug (the end of extension treatment period), or the date of initiation of another investigational agent or hormonal therapy or surgical intervention or entering the MVT-601-035 study, whichever occurs first. Serious adverse events reported to the investigator after the safety reporting period should be reported to the sponsor if the investigator assesses the event as related to study drug.

The severity of all treatment-emergent adverse events will be evaluated by the investigator based on the National Cancer Institute's Common Terminology Criteria for Adverse Events (CTCAE) and will be coded to preferred term and system organ class using MedDRA 22.0 or higher.

A treatment-emergent adverse event is defined as any adverse event that occurs after administration of the first dose of parent study drug.

Adverse event summaries will be based on treatment-emergent adverse events in the parent and extension studies, unless otherwise specified. All adverse events in the parent and extension studies will be listed in by-patient listings.

The following tabular summaries that include the number and percentage of patients will be provided:

- Overview of adverse events;
- All adverse events;
 - By SOC and PT;
 - By decreasing frequency of PT;
 - By SOC, PT, and maximum severity;
 - Study drug-related per investigator by SOC and PT;
 - By time to onset, SOC and PT;
- Grade 3 or above adverse events;
 - By SOC and PT;
 - By decreasing frequency of PT;
 - Study drug-related per investigator by SOC and PT;
- Grade 2 or above adverse events;
 - By SOC and PT;
 - By decreasing frequency of PT;
 - By SOC, PT, and maximum severity;

- Study drug-related per investigator by SOC and PT;
- Adverse events leading to study drug withdrawal;
 - By SOC and PT;
 - By decreasing frequency of PT;
- Adverse events leading to dose interruption;
 - By SOC and PT;
 - By decreasing frequency of PT;
- Adverse events resulting in fatal outcome;
 - By decreasing frequency of PT;
- Serious adverse events;
 - By SOC and PT;
 - By decreasing frequency of PT;
 - By SOC, PT, and maximum severity;
 - By SOC, PT, and relationship to study drug;
- Adverse events of clinical interest (ALT or AST $\geq 3 \times$ ULN);
 - By SOC, PT, and maximum severity;
 - By decreasing frequency of PT.

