9.1.8. Exposure-adjusted Adverse Events

Adverse events by time to onset and an exposure-adjusted adverse event analysis will be provided. The exposure-adjusted adverse event rate will be summarized by system organ class and preferred term for each parent study treatment group, where the exposure-adjusted adverse event rate is calculated as number of patients with a particular adverse event by total exposure-time among patients at risk of an initial occurrence of the event. Exposure-time is derived as exposure to any study drug throughout the parent and extension study.

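### The exposure-adjusted adverse event rate in SAP 9.1.8 counts first events up to about 30 days after the last dose but only time on drug, which modestly inflates it for women who do not enter MVT-601-035

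*SAP*

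**What the plan says.** SAP 9.1.8 defines the rate as the "number of patients with a particular adverse event by total exposure-time among patients at risk of an initial occurrence of the event", by system organ class and preferred term within each parent-study group. It then states: "Exposure-time is derived as exposure to any study drug throughout the parent and extension study". SAP 4.3.5 runs overall treatment duration "from the date of the first dose of parent study drug to the date of the last dose of extension study drug as follows", so time stops at the last dose.

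SAP 9.1 defines a treatment-emergent event as "any adverse event that occurs after administration of the first dose of parent study drug", with no upper limit, and bases the adverse event summaries on these events unless a section says otherwise. SAP 9.1.8 does not. Collection runs to the safety follow-up visit about 30 days after the last dose, or ends earlier at another investigational agent, hormonal therapy, "surgical intervention or entering the MVT-601-035 study, whichever occurs first". Protocol 9.5 likewise runs the treatment-emergent period to about 30 days after the last dose.

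SAP 2.1 places entry into MVT-601-035 at the Week 52 visit, for eligible women who complete the study. Protocol 6.4 describes that study as one "which will enroll patients who responded to study treatment".

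**The concern.** An exposure-adjusted rate is meant to remove the effect of unequal observation, so its events and its time must come from the same period. Here a first event two weeks after the last dose counts, but the two weeks do not.

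The mismatch does not fall evenly. Women who roll over leave collection at about the last dose. All post-dose events therefore come from early discontinuers and from completers who do not continue. Continuation depends on completion and response, so the excess in each parent-study group is tied to efficacy and retention rather than to harm on drug. At stake is the reading of one descriptive safety table presented side by side for three groups.

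**Working it through.** The plan states no expected rate and no rollover share, so there is no figure of its own to reproduce. The check compares the SAP 9.1.8 rate with a rate whose events and time cover the same period.

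**Inputs**
- Treatment time T = 365 days (Week 52 target day, SAP Table 2). SAP 6 counts placebo as study drug, so T applies to all three groups. Extension dosing starts the day after the last parent-study dose, so the only planned off-drug period is at the end.
- Post-dose collection F = 30 days. The visit window of −3 to +18 days (Protocol Table 1) gives 27 to 48 days. F is about 0 for women who roll over; SAP Table 2 also closes their Week 52 window one day after the last dose.
- Rollover share r: not in the documents, so assumed.
- Hazard: assumed constant on drug and shortly after it.

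**Rare events, one woman who does not roll over.** Excess = F/T.

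| Last dose | F = 27 | F = 30 | F = 48 |
|---|---|---|---|
| Day 365 (completer) | 7.4% | 8.2% | 13.2% |
| Day 253 (Week 36) | 10.7% | 11.9% | 19.0% |
| Day 197 (Week 28) | 13.7% | 15.2% | 24.4% |

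For a woman who rolls over the excess is 0%.

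**Group level, completers.** Excess = (1 − r) × 30/365.
- r = 25%: 0.75 × 8.2% = 6.2%
- r = 50%: 4.1%
- r = 75%: 0.25 × 8.2% = 2.1%

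Two groups with the same true rate and shares of 25% and 75% would show a ratio of 1.062/1.021 = 1.04.

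**Common events.** Only a first occurrence counts, so a post-dose recurrence adds nothing. With no rollover and hazard λ, the ratio to the matched rate is (1 − e^(−λ(T+F))) / (1 − e^(−λT)). At 10% incidence over T, λT = 0.1054 and λ(T+F) = 0.1140, so the ratio is 0.1078/0.1000, an excess of 7.8%. At 30% incidence it is 0.3202/0.3000, an excess of 6.7%.

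**Different hazard after stopping** (rare events, completer, r = 0). Half the on-drug hazard gives 4.1%, double gives 16.4%, and no post-dose events gives 0%.

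**Time not cut at the first event.** SAP 9.1.8 does not say whether it is. At 20% incidence, r = 0 and uncut time, the reported rate is 0.2145/T against a true hazard of 0.2231/T, which is 3.9% too low. A matched but uncut rate would be 0.2000/T, so the post-dose events still raise the figure by 7.3%.

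**The case against.** The strongest reply is that little depends on this. SAP 7.1 plans no formal treatment comparison, incidence is the stated safety endpoint, SAP 9.1.8 also plans events by time to onset, and SAP 5.1 will report MVT-601-035 enrolment by parent-study group. All of that stands and limits the importance of the point. It does not align the two periods.

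The 8% is also close to a ceiling for a day-30 visit at constant hazard. It is the rare-event limit, and hormonal therapy, another agent or surgery can end collection before day 30. This stands. The upper figures apply only to women seen on the last day of the window with none of these.

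SAP 9.1 labels the follow-up visit as the end of the extension treatment period, which might suggest that follow-up time is included. It does not help, because SAP 9.1.8 uses exposure to drug rather than that period.

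Four stronger readings are tempting, and the documents do not support them:
- **The rate is too high in absolute terms.** If time is not cut at the first event, the reported rate for a common event can lie below the true hazard. The supported claim is inflation relative to a matched rate.
- **The groups will differ materially.** No rollover share is given, and all groups receive the same open-label treatment. Even the assumed 25% against 75% yields only about 4%.
- **Events during MVT-601-035 would be collected here.** SAP 2.1 says: "Patients who enroll directly into the MVT-601-035 study upon completion of the Week 52 visit will have the Follow-up visit". Protocol 6.3 says: "for patients who enroll directly into another relugolix clinical study upon completion of the Week 52 visit, then the Follow-up visit may be waived". This is a real conflict of wording, but SAP 9.1 ends collection at entry, so it does not bear on the rate.
- **The table of events first arising in the extension is biased and should stop at the last dose.** That table counts patients and has no exposure denominator. Cutting it would depart from the 30-day treatment-emergent period in Protocol 9.5.

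**Conclusion.** The mismatch is real and modest. SAP 9.1.8 admits first occurrences from a post-dose period that its denominator omits, and only women who do not enter MVT-601-035 contribute them. The direction needs only that some first events begin after the last dose. The size rests on the constant hazard, the rare-event approximation and the visit timing shown above, and the between-group effect rests on assumed rollover shares. No trial conclusion turns on it. The definition should still be corrected, because adjusting for unequal observation is the table's only purpose.

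**What to change.** In SAP 9.1.8, count only patients whose first occurrence begins between the first and last dose of study drug, and state that each patient's time is cut at that first event. Report events beginning after the last dose in a separate table for women who did not enter MVT-601-035, with their follow-up days as the denominator.

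An equally valid alternative keeps all treatment-emergent events and adds each woman's at-risk post-dose collection time to the denominator. It should carry the same statement on cutting time.

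Leave the count table of events first arising in the extension as it is, with a footnote that collection ends earlier for women who roll over.

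As a separate correction, reconcile SAP 2.1 with Protocol 6.3 and SAP 9.1 and 3.3 on the Follow-up visit for these women.

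The cost is SAP wording plus, under the first option, one table. Onset and last-dose dates are already used in the SAP, so no new data are needed, and the SAP introduction allows changes before database lock. Under the first option post-dose events leave the exposure-adjusted table; under the second they stay, and the result is a rate over treatment plus follow-up rather than over treatment alone.

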9.2. Laboratory Data

Laboratory parameters, including chemistry and hematology panels, specified as per protocol for the parent and extension studies, and collected from the central laboratory will be tabulated and presented in by-patient listings. Urinalysis and hepatitis virus serological test results will be provided in by-patient listing only.

The National Cancer Institute CTCAE Grading Scale with numeric component will be used to categorize toxicity grade for laboratory parameters (CTCAE v5.0, dated 27 Nov 2017). Parameters that have criteria available for both low and high values (eg, hypercalcemia for a high value of calcium and hypocalcemia for a low value of calcium) will be summarized for both criteria (low and high). Patients will only be counted once for each criterion. The same patient can be counted for both criteria if she has laboratory values meeting each criterion. Shift tables will be provided for each gradable parameter to summarize Baseline toxicity grade versus worst post-Baseline toxicity grade throughout the parent and extension studies. For laboratory parameters that are not gradable by the CTCAE, a shift table based upon the normal range (low,

normal, and high) will be provided for each parameter to summarize the Baseline versus worst post-Baseline results throughout the parent and extension studies.

Boxplots of laboratory values over time, including visits in both the parent study and extension study, will be plotted for key laboratory parameters. These laboratory parameters include, but are not limited to, hematology (hemoglobin, platelets, leukocytes, neutrophils), creatinine, glomerular filtration rate, and hepatic function panel (alanine aminotransferase [ALT], aspartate aminotransferase [AST], alkaline phosphatase [ALP], and total bilirubin).

The change from Baseline to each post-Baseline study visit will be presented by parent study treatment group for each laboratory test in both tables and figures.

The number and proportion of patients with liver test elevations will be presented by parent study treatment group. Liver test elevations are assessed by using post-Baseline results for ALT, AST, ALP, and total bilirubin based on the definitions presented in [Table 13](#).

Table 13: Categories of Liver Test Elevations

Laboratory Test	Category
ALT or AST	ALT or AST > ULN < 3 × ULN ALT or AST ≥ 3 × to < 5 × ULN ALT or AST ≥ 5 × to < 10 × ULN ALT or AST ≥ 10 to < 20 × ULN ALT or AST ≥ 20 × ULN
Total bilirubin	Total bilirubin > 2 × ULN
ALT or AST and total bilirubin	ALT or AST ≥ 3 × ULN + total bilirubin > 2 × ULN
ALT or AST, total bilirubin, and ALP	ALT or AST ≥ 3 x ULN + total bilirubin > 2 × ULN + ALP < 2 × ULN

Abbreviations: ALP = alkaline phosphatase; ALT = alanine aminotransferase; AST = aspartate aminotransferase; ULN = upper limit of normal.

The number and percentage of patients with concurrent (defined as measurements on the same day) ALT or AST ≥ 3 × ULN and total bilirubin > 2 × ULN will also be presented.

Selected chemistry and hematology test results meeting pre-defined limits of change at any time and based on last observation on treatment will be also summarized per pre-defined threshold (refer to [Appendix 1](#)) by parent study treatment group.

